- NSAD (Northstar Assessment for Dysferlinopathy)—AMB
- 6 min walk test and 10 meter timed run test, if patient ambulatory
- PUL (Performance of Upper Limb)
- Brooke Scale
- Vignos Scale

Strength assessments

- MMT MRC

Patient Reported Outcome Measures

- PROM: ACTIVLM
- Quality of life questionnaire

Blood and urine for exploratory biomarkers

Imaging

- MRI/ MRS of leg and arm muscles to measure muscle volume, T2 value and fat fraction
- DEXA scan at screening and at 6 months

Outcome measures:

- Comparing MRI/MRS changes the leg and arm muscles at screening and 6 months
- Change in 6 min walk test and 10 meter timed run test for ambulatory patients
- Change in strength assessment
- Change in FVC measurements

Strength assessment:

- MRC scale: Shoulder abduction, elbow flexion, knee extension and knee flexion, hip flexion, foot dorsiflexion.
- Grip strength (Jamar dynamometer)

- Hand held dynamometry

Functional testing:

- Lift arm above head
- Lift arm above head using 50g/100g/200g/500g weight
- Bring arm to the mouth
- Bring weight to mouth using 50g/100g/200g/500g weight

STUDY INTERVENTION(S) / INVESTIGATIONAL AGENT(S):

Oral prednisone is a synthetic glucocorticoid that is FDA-approved medication for the treatment of various inflammatory and allergic conditions.

In this study, subjects will be asked to take weekly GC oral prednisone, dosed based on weight (1mg/kg for patients who weigh less than or equal to 70 kg and 0.75 mg/kg for patients who weigh more than 70 kg). Subjects will be instructed to take weekly prednisone on Mondays after their last meal between 7 and 9 PM. Study drug, oral prednisone, will be stored under the secure and controlled environment of the Investigational Drug Pharmacy at Northwestern Memorial Hospital. The Investigational Drug Pharmacy will follow its current SOP regarding the storage and handling of investigative drugs. The study drug will be dispensed from the Pharmacy and administered to subjects once they have signed informed consent, passed screening, on Day 0 of their treatment. Subjects will return home with 6 months of study drug treatment. They will be educated on dosing, storage, and return of unused study drug by the study staff. Subjects will be contacted on a monthly basis to assess medication and dosing adherence. They will be asked to confirm their medication and the dosing instructions and re-educated if not adhering.

PROCEDURES INVOLVED:

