The subject will be asked to undergo an MRI through the study team at the Center for Translational Imaging at Northwestern University. Before the study participant completes the MRI, he or she must answer questions about their medical and surgical history on a MRI safety questionnaire to determine whether it will be safe for them to complete the MRI. If not, they will not be eligible to participate in this study. No contrast will be administered. The MRI images will be de-identified and electronically transmitted to a secure file transfer (SFT) system to the University of Florida for interpretation.

Before dosing occurs, a member of the study team (physical or occupational therapist) will complete the following functional assessments: Northstar Assessment for Dysferlinopathy (NSAD) –AMB, 10 meter timed run test and 6-minute walk test if the patient is ambulatory, performance of upper limb (PUL) evaluation, Brookes and Vignos scales. A member of the study team will also collect the strength assessment, MMT MRC.

Subjects will be asked to complete two questionnaires; ACTIVLM and a Quality of Life Questionnaire.

The subject will also complete a bone density (DEXA) scan at Northwestern Memorial Hospital.

Monthly Phone Calls

Between Day 0 and Month 6, a member of the study team will call the subjects on a monthly basis to determine their state of health and whether they are taking the medication correctly. State of health will be determined by assessed by asking if the subject has experienced any changes to their physical health (adverse events). He or she will also ask the subjects about how they are taking the medication and if you are doing so correctly. If the subjects are not, the study member will help the subjects by providing additional instructions on how to correctly take the study drug.

Month 6

After 6 months of treatment, subjects will return to the MDA Clinic at Northwestern Memorial Hospital. A member of the study team will collect vital signs, weight and height, medical history, concomitant medication information, and review adverse events. The subject will also provide a sample for safety laboratory analysis (Comprehensive chemistry panel, hemoglobin A1C, CK, and lipid panel). A blood and urine sample will be taken for exploratory biomarkers.

A member of the study team will also collect forced vital capacity in a sitting and supine position.

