A member of the study team (physical or occupational therapist) will complete the following functional assessments: Northstar Assessment for Dysferlinopathy (NSAD) –AMB, 10 meter timed run test and 6-minute walk test if the patient is ambulatory, performance of upper limb (PUL) evaluation, Brookes and Vignos scales. A member of the study team will also collect the strength assessment, MMT MRC.

Subjects will be asked to complete two questionnaires; ACTIVLM and a Quality of Life Questionnaire.

The subject will also complete a bone density (DEXA) scan at Northwestern Memorial Hospital.

An MRI will be conducted at the Center for Translational Imaging at Northwestern University within 2 weeks before or after the subject’s final visit. No contrast will be administered.

An overview of the study assessments may be found in Table 1.0 below:

| | Screening (D0-2M) | Day 0 | M6 +2 wks |
|--------------------------------------|-------------------|-------|-----------|
| Informed Consent | X | | |
| Demographics | X | | |
| Vital Signs | X | X | X |
| Weight and Height | X | X | X |
| Medical History | X | X | X |
| Concomitant Medications | X | X | X |
| Genetic mutation Confirmation | X | | |
| Review EKG* | X | | |
| Review Echo** | X | | |
| Safety Monitoring Labs*** | | X | X |
| Forced Vital Capacity (FVC) | | X | X |
| NSAD | | X | X |
| 6-min Walk Test / 10 m Run | | X | X |
| Performance of Upper Limb | | X | X |
| Brooke Scale | | X | X |
| Vignos Scale | | X | X |
| MMT MRC | | X | X |
| Grip Strength | | X | X |
| ACTIVLM | | X | X |
| Quality of Life Questionnaire (SF36) | | X | X |
| MRI/MRS | | X | X |
| DEXA Scan | | X | X |
| Study Drug Dispensation | | X | |
| Review of Adverse Events | | | X |

Table 1.0: Schedule of Assessments from Screening, Day 0, and Month 6

* EKG – Results within 2 months of study initiation accepted

**Echo – Results within 6 month of study initiation accepted

*** Comprehensive chemistry panel, hemoglobin A1C, CK, lipid panel

SHARING RESULTS WITH PARTICIPANTS

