7. A diagnosis of congestive heart failure
8. A diagnosis of chronic kidney disease
9. A diagnosis of untreated hypothyroidism
10. The patient is believed to be at high risk of osteoporosis by the primary investigator
11. Inability to provide consent
12. Prior oral glucocorticoid steroid use for > than one month during a subject's life.
13. Full time ventilator dependency
14. Heart failure symptoms or LVEF <25%
15. Orthopedic surgery within the prior year or upcoming elective orthopedic surgery within the 6-months from Day 0.
16. Inability to complete MRI (claustrophobia, metal implants)
17. Pregnant women at screening, women seeking to become pregnant, or men seeking to father a child within 6-months from Day 0 should not participate in this study.

PARTICIPANT POPULATION(S)

| Accrual Number: | Category/Group: (Adults) | Consented: Maximum Number to be Consented or Reviewed/Collected/Screened | Enrolled: Number to Complete the Study or Needed to Address the Research Question |
|-----------------|--------------------------|--|---|
| Total: | 50 adults | 40 adults | 30 adults |

RECRUITMENT METHODS

All subjects will be recruited through the Muscular Dystrophy (MDA) clinic at Northwestern Memorial Hospital. The MDA clinic is located in the [name] and is held on Wednesday mornings from 08:00-12:00.

Participants will be selected by the neurologists in the MDA clinic, primarily the Principal Investigator. They will be selected for screening based on their clinical exam, medical history, and willingness to participate in the study. The Principal Investigator will review the patient's medical chart to determine pre-eligibility. A member of the study team will conduct the informed consent process once pre-eligibility is confirmed by the Principal Investigator.

No external methods will be used for recruitment purposes.

COMPENSATION FOR PARTICIPATION IN RESEARCH ACTIVITIES

Subjects will not be compensated for participating in this study. Furthermore, subjects will not be reimbursed for expenses related to travel, lodging, or accommodation.

If patients become ill or are injured as a result of this study (medications, devices or procedures), they should seek medical treatment through their doctor or treatment center of choice. The subject should promptly tell his/her study doctor about any illness or injury.

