The hospital [university, researchers] will not pay for medical care required because of a bad outcome resulting from your participation in this research study. This does not keep you from seeking to be paid back for care required because of a bad outcome.

WITHDRAWAL OF PARTICIPANTS

Subjects may be withdrawn from the study if the Principal Investigator believes that participating places them at risk of harm. Subjects may also be withdrawn if it is found that they are not complying with the study's required dosing instructions.

In the event that a subject is to be withdrawn, the Principal Investigator will inform the subject regarding the reason for withdrawal. The Principal Investigator will make recommendations for seeking additional testing and prompt medical care, if necessary. A member of the study team will indicate that the subject was withdrawn in the subject binder.

RISKS TO PARTICIPANTS

Participating in this study places subjects at minimal risk of the following:

Risks from glucocorticoid steroids

- The risks associated with glucocorticoid steroids include: glaucoma (elevated pressure in the eyes), edema (fluid retention in lower legs), hypertension (high blood pressure), weight gain, problems with mood and memory, alterations in endocrine function, increased risks related to infections, decrease in bone density, and possible damage to your vision. These risks are seen when people take glucocorticoid steroids daily for extended periods of time. Based on preclinical studies in animals and limited studies in humans, it is expected these risks are much less when taking glucocorticoids steroids once per week.

Since the subjects will be taking glucocorticoid steroids once weekly, for 6 months, their risk of side effects is low, with short duration, and reversible.

Risk from blood draws

The risks of taking blood include pain, a bruise at the point where the blood is taken, redness and swelling of the vein and infection, and a rare risk of fainting.

Risk from MRI

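### The withdrawal rule takes subjects out of the study, not only off prednisone, for judged harm or non-compliance, with no exit assessment, so Month 6 safety measurements could be missing selectively.

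*Protocol*

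**What the plan says.** Under WITHDRAWAL OF PARTICIPANTS the protocol gives two grounds. The first is "Subjects may be withdrawn from the study if the Principal Investigator believes that participating places them at risk of harm". The second is "Subjects may also be withdrawn if it is found that they are not complying with the study's required dosing instructions". The first speaks of the study, not of the drug, and the second follows on from it. Stopping prednisone while remaining under observation is not mentioned.

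Three steps follow a withdrawal. The subject is told the reason. Advice is given: "The Principal Investigator will make recommendations for seeking additional testing and prompt medical care, if necessary". The fact of withdrawal is noted in the subject binder. None of these is a study measurement, and the text does not ask for the reason to be written down.

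Safety is the primary outcome under STUDY ENDPOINTS, monitored by a laboratory panel, FVC and monthly calls. DEXA is listed there under imaging and is not part of the primary safety list. PROCEDURES INVOLVED describes three visits: screening, Day 0 and Month 6. Table 1.0 places the labs, FVC and DEXA at Day 0 and Month 6 only. Between those visits, "a member of the study team will call the subjects on a monthly basis to determine their state of health" and to check dosing. For subjects who are not adhering, the intervention section says: "They will be asked to confirm their medication and the dosing instructions and re-educated if not adhering".

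DATA MANAGEMENT AND CONFIDENTIALITY describes a single-arm pilot that compares entry with 6 months of treatment and will inform a larger trial.

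**The concern.** Both grounds for withdrawal bear on the question the trial asks. A subject judged to be at risk is more likely than others to carry safety information, and a subject who skips doses has had a different exposure. If either leaves the study before Month 6, the second lab panel, FVC and DEXA are not scheduled for that subject. The Month 6 data then describe those who were neither judged at risk nor found non-compliant.

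There is no control arm in which similar losses could be seen. Labs and FVC are the measured part of the primary outcome, and phone calls cannot show a change in HbA1c, lipids, chemistry, FVC or bone density. A statistical analysis plan, which is not at hand, may say how missing values are handled, but it cannot supply measurements that were never made.

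**Working it through.** The protocol gives no withdrawal rate, and its sample size of 30 comes with no attrition assumption. There is therefore no stated figure to reproduce. The check is first a reading of the sections together, then one labelled illustration.

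**Tracing one subject.** Suppose a subject is withdrawn at Month 3.

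| Item | Source in the protocol | Available for this subject? |
|---|---|---|
| Labs and FVC before dosing | Table 1.0, Day 0 | Yes |
| DEXA before dosing | Table 1.0, Day 0 | Yes |
| Calls on health and dosing, up to withdrawal | Monthly Phone Calls | Yes |
| Note that the subject was withdrawn | WITHDRAWAL OF PARTICIPANTS | Yes |
| Labs or FVC after dosing | Table 1.0, Month 6 only | None scheduled |
| DEXA after dosing | Table 1.0, Month 6 only | None scheduled |
| Exit visit or off-drug follow-up | None found in any section | No |

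A change from entry cannot be formed for this subject on labs, FVC or DEXA.

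**Illustration of size.** Inputs:
- N = 30 dosed. This takes the stated sample size as the number dosed. The accrual table's column heading, "Enrolled: Number to Complete the Study or Needed to Address the Research Question", leaves open whether 30 is the number completing.
- w = 5 subjects withdrawn and unmeasured. This is assumed.
- A yes/no abnormality at Month 6. This is assumed; the protocol defines none.
- No abnormality among those measured. This is assumed.

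Measured subjects: 30 − 5 = 25, so the report reads 0/25 = 0%.

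Exact (Clopper-Pearson) two-sided 95% upper limit for 0/n: 1 − 0.025^(1/n) = 1 − 0.025^(1/25) = 0.137. The interval is 0% to 13.7%.

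Range for the proportion among all 30, given the 25 measured:
- lowest, if none of the 5 is abnormal: 0/30 = 0%
- highest, if all 5 are abnormal: 5/30 = 16.7%

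The two ranges answer different questions and should not be set against each other. The first is sampling uncertainty and treats the 25 as representative. The second is what is unknown about these 30 subjects because 5 were not measured. Its upper end is an arithmetic bound, not a prediction: some of the 5 might be non-compliers with little exposure.

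**The case against.** The strongest reply is that this is largely silence in the text. Both sentences say that subjects may be withdrawn. Neither requires it, neither forbids stopping the drug alone, and neither forbids measuring someone at Month 6 who is off drug. Re-education is the described response to non-adherence. This stands, and it makes the loss possible rather than certain. It does not remove the gap, because the only stated action for harm is removal from the study and nothing is scheduled afterwards.

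Second, harm is not lost from view. No labs, FVC or DEXA are scheduled between Day 0 and Month 6, so a withdrawal for harm would usually follow something reported on a call or to the study doctor. In a pilot of safety and tolerability, such a withdrawal is itself a result. This also stands. What is missing is the subject's second measurement, not the knowledge that the subject was withdrawn.

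Third, DATA MANAGEMENT AND CONFIDENTIALITY gives the team access to the hospital's electronic record. Testing advised at withdrawal might be retrievable if it were done at that hospital. This is a partial safeguard. The testing is advised only where needed, has no set content, and may be done elsewhere.

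Fourth, the illustration is not on the trial's own scale, since the planned comparison is entry against 6 months. That is correct, and the illustration serves only to show scale.

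A reader might infer that the rule will make prednisone look safer than it is. The documents do not support a direction: subjects withdrawn for harm may have worse values, while those who skipped doses had less exposure. A reader might also infer that withdrawn subjects are replaced until 30 complete, or that as many as 40 could be dosed. The protocol states no replacement. The 40 is a maximum to be consented, with eligibility decided after consent.

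**Conclusion.** The point holds as a modest gap in trial conduct. Following the protocol as written can leave subjects who are withdrawn for harm or non-compliance without any scheduled post-dose labs, FVC or DEXA. The Month 6 comparison could then rest on a group selected on harm or adherence. The loss could not be repaired at analysis.

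Its frequency and direction are unknown, and if nobody is withdrawn early there is no effect. The illustrated gap of 0% to 16.7% among 30 depends entirely on the assumed 5 unmeasured subjects and the assumed binary finding. The change is worth making because it is cheap and protects the primary outcome. The documents do not show that the trial's safety conclusions would be wrong.

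**What to change.** Amend WITHDRAWAL OF PARTICIPANTS so that judged harm or non-compliance may stop study drug but does not by itself end follow-up. With the subject's agreement:

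- Continue the monthly calls and the Month 6 labs and FVC.
- Do the Month 6 DEXA unless it is contraindicated, for example in pregnancy.
- If the subject will not stay, do these assessments once on leaving, in place of Month 6. DEXA then remains at two scans, 2 × 4 = 8 mrem, the total already stated.
- Write the reason for stopping in the subject binder.
- Report safety for all dosed subjects, and also show the values of subjects off drug separately.

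The cost is protocol wording and the follow-up of those who stop. The calls and the Month 6 visit are already planned for everyone. An assessment on leaving may need an unscheduled visit by a subject who receives no travel reimbursement. Month 6 values taken off drug reflect reduced exposure, which is why they need to be shown separately as well as within the whole.
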